6.1.1. Administration

In both periods, study intervention will be administered following breakfast, as described in [Section 5.3.2](#), and according to the SAI.

In **Period 1**, oral dose of [¹⁴C]PF-07081532, 30 mg (250 nCi) will be administered as an extemporaneously prepared liquid formulation, approximately 10 minutes after completion of breakfast.

In **Period 2**, unlabeled oral dose of PF-07081532, 30 mg will be administered as an extemporaneously prepared liquid formulation, approximately 10 minutes after completion of breakfast. Approximately 1 hour after the administration of the unlabeled oral dose, a single dose of [¹⁴C]PF-07081532, 100 µg (250 nCi) will be administered IV, as an infusion over approximately 15 minutes.

Administration of labeled and unlabeled PF-07081532 via oral and IV dosing routes will be performed by qualified investigator site personnel (in accordance with local regulations and laws). Please refer to the SAI for further details.

6.2. Preparation, Handling, Storage, and Accountability

1. The investigator or designee must confirm that appropriate conditions (eg, temperature) have been maintained during transit for all study interventions received and any discrepancies are reported and resolved before use of the study intervention.
2. Only participants enrolled in the study may receive study intervention and only authorized site staff may supply, prepare, and/or administer study intervention.
3. All study interventions must be stored in a secure, environmentally controlled, and monitored (manual or automated recording) area in accordance with the labeled storage conditions with access limited to the investigator and authorized site staff. At a minimum, daily minimum and maximum temperatures for all site storage locations must be documented and available upon request. Data for nonworking days must indicate the minimum and maximum temperatures since previously documented upon return to business.
4. Any excursions from the study intervention label storage conditions should be reported to Pfizer upon discovery along with actions taken. The site should actively pursue options for returning the study intervention to the labeled storage conditions, as soon as possible. Once an excursion is identified, the study intervention must be quarantined and not used until Pfizer provides permission to use the study intervention. Specific details regarding the excursion definition and information to report for each excursion will be provided to the site by the sponsor.
5. Any storage conditions stated in the SRSD will be superseded by the storage conditions stated on the label.

6. Study interventions should be stored in their original containers.
7. The investigator, institution, head of the medical institution (where applicable), or authorized site staff is responsible for study intervention accountability, reconciliation, and record maintenance (ie, receipt, reconciliation, and final disposition records).
8. Further guidance and information for the final disposition of unused study interventions are provided by the sponsor. All destruction must be adequately documented. If destruction is authorized to take place at the investigator site, the investigator must ensure that the materials are destroyed in compliance with applicable environmental regulations, institutional policy, and any special instructions provided by Pfizer.

Upon identification of a product complaint, notify the sponsor within 1 business day of discovery.

6.2.1. Preparation and Dispensing

Within this protocol, preparation refers to the investigator site activities performed to make the study intervention ready for administration or dispensing to the participant by qualified staff. Dispensing is defined as the provision of study intervention, concomitant treatments, and accompanying information by qualified staff member(s) to a healthcare provider, participant in accordance with this protocol. Local health authority regulations or investigator site guidelines may use alternative terms for these activities.

Unlabeled PF-07081532 and [¹⁴C]PF-07081532 oral dosing formulations will be prepared in the CRU by 2 trained personnel and QP. Details of dose preparation will be given in a separate EDR. The prepared doses will be provided in unit dose containers and labeled in accordance with Pfizer regulations and the investigator site's labeling requirements.

[¹⁴C]PF-07081532 formulation for IV administration will be manufactured at the CRU by 2 trained personnel and QP-released prior to administration. Details of the dose preparation will be provided in a separate TA. The prepared doses will be provided in unit dose containers and labeled in accordance with Pfizer regulations and the investigator site's labeling requirements.

6.3. Assignment to Study Intervention

Following completion of informed consent at the screening visit, each participant will be assigned an 8-digit SSID number, by the site staff. The first 4 digits of the SSID will reflect the sponsor-assigned site number and the remaining 4 digits will reflect each participant's unique number assigned in chronological order as informed consent is obtained. **In addition**, on Day 1, each participant who is dosed with the study intervention will be assigned a separate, distinct number (as provided to the site by the sponsor at the start of the study) to enable execution of sponsors' standard processes for analysis of all PK-related samples.

6.4. Blinding

This is an open-label study.

6.4.1. Blinding of Participants

Participants will be unblinded to their assigned study intervention.

6.4.2. Blinding of Site Personnel

Investigators and other site staff will be unblinded to participants' assigned study intervention.

6.4.3. Blinding of the Sponsor

Sponsor staff will be unblinded to participants' assigned study intervention.

6.5. Study Intervention Compliance

When the individual dose for a participant is prepared from a bulk supply, the preparation of the dose will be confirmed by a second qualified member of the study site staff.

When participants are dosed at the site, they will receive study intervention directly from the investigator or designee, under medical supervision. The date and time of each dose administered in the clinic will be recorded in the source documents and recorded in the CRF. The dose of study intervention and study participant identification will be confirmed at the time of dosing by a member of the study site staff other than the person administering the study intervention. Study site personnel will examine each participant's mouth to ensure that the oral dose of study intervention was ingested.

See the site administration instructions for instructions on how to prepare the study intervention for administration. Study intervention should be prepared and dispensed by an appropriately qualified and experienced member of the study staff (eg, physician, nurse, physician's assistant, nurse practitioner, pharmacy assistant/technician, or pharmacist) as allowed by local, state, and institutional guidance.

6.6. Dose Modification

Dose modification of PF-07081532 is not permitted.

6.7. Continued Access to Study Intervention After the End of the Study

No study intervention will be provided to participants at the end of their study participation.

6.8. Treatment of Overdose

For this study, any dose of PF-07081532 greater than 1.6 g within a 24-hour time period is projected to result in exposure that will exceed that observed at the NOAEL in the pivotal 9-month toxicology study in monkeys, after accounting for species difference in plasma protein binding, and thus will be considered an overdose.

There is no specific treatment for an overdose.

In the event of an overdose, the investigator/treating physician should:

1. Contact the study medical monitor within 24 hours.
2. Closely monitor the participant for any AEs/SAEs and laboratory abnormalities as medically appropriate and at least until the next scheduled follow-up.
3. Document the quantity of the excess dose as well as the duration of the overdose in the CRF.
4. Overdose is reportable to Pfizer Safety **only when associated with an SAE**.
5. Obtain a blood sample for PK analysis within 3 days from the date of the last dose of study intervention if requested by the study medical monitor (determined on a case-by-case basis).

6.9. Prior and Concomitant Therapy

Use of any prescription or non-prescription drugs and dietary and herbal supplements are prohibited within 7 days or 5 half-lives (whichever is longer) prior to the first dose of study intervention or as outlined in [Appendix 10](#) specifically for medications prohibited due to potential DDI. Participants will abstain from all concomitant treatments during the study, except for the treatment of AEs. Limited use of non-prescription medications that are not believed to affect participant safety or the overall results of the study **may be permitted on a case-by-case basis following approval by the sponsor** and as long as they are not listed in [Appendix 10](#). Use of dietary fiber supplementation, prune juice or non-prescription medications (eg, milk of magnesia, docusate) specifically used as needed to promote bowel movement (see [Section 5.3.2.1](#)) is allowed at investigator's discretion and such use should be recorded. Acetaminophen/paracetamol may also be used at doses of ≤ 1 g/day.

All concomitant treatments taken during the study must be recorded with indication, daily dose, and start and stop dates of administration. All participants will be questioned about concomitant treatment at each clinic visit.

Treatments taken within 28 days before the first dose of study intervention will be documented as a prior treatment. Treatments taken after the first dose of study intervention will be documented as concomitant treatments.

6.9.1. Rescue Medicine

There is no rescue therapy to reverse AEs observed with PF-07081532; standard medical supportive care must be provided to manage any AEs.

7. DISCONTINUATION OF STUDY INTERVENTION AND PARTICIPANT DISCONTINUATION/WITHDRAWAL

7.1. Discontinuation of Study Intervention

It may be necessary for a participant to permanently discontinue study intervention. Reasons for permanent discontinuation of study intervention include the following: safety, behavioral, compliance, or administrative reasons, or if the study is terminated by sponsor.

Note that discontinuation of study intervention does not represent withdrawal from the study. If study intervention is permanently discontinued, the participant should remain in the study to be evaluated for safety and PK, if possible. See the [SoA](#) for data to be collected at the time of discontinuation of study intervention and follow-up for any further evaluations that need to be completed.

In the event of discontinuation of study intervention, it must be documented on the appropriate CRF/in the medical records whether the participant is discontinuing further receipt of study intervention or also from study procedures, posttreatment study follow-up, and/or future collection of additional information.

7.2. Participant Discontinuation/Withdrawal From the Study

A participant may withdraw from the study at any time at their own request. Reasons for discontinuation from the study include the following: safety, behavioral, compliance or administrative reasons, or if the study is terminated by sponsor.

At the time of discontinuing from the study, if possible, an early discontinuation visit should be conducted. See the [SoA](#) for assessments to be collected at the time of study discontinuation and follow-up and for any further evaluations that need to be completed.

The early discontinuation visit applies only to participants who are enrolled and then are prematurely withdrawn from the study. Participants should be questioned regarding their reason for withdrawal.

The participant will be permanently discontinued from the study intervention and the study at that time.

If a participant withdraws from the study, they may request destruction of any remaining samples taken and not tested, and the investigator must document any such requests in the site study records and notify the sponsor accordingly.

If the participant withdraws from the study and also withdraws consent (see [Section 7.2.1](#)) for disclosure of future information, no further evaluations will be performed and no additional data will be collected. The sponsor may retain and continue to use any data collected before such withdrawal of consent.

7.2.1. Withdrawal of Consent

Participants who request to discontinue receipt of study intervention will remain in the study and must continue to be followed for protocol-specified follow-up procedures. The only exception to this is when a participant specifically withdraws consent for any further contact with them or persons previously authorized by the participant to provide this information. Participants should notify the investigator in writing of the decision to withdraw consent from future follow-up, whenever possible. The withdrawal of consent should be explained in detail in the medical records by the investigator, as to whether the withdrawal is only from further receipt of study intervention or also from study procedures and/or posttreatment study follow-up, and entered on the appropriate CRF page. In the event that vital status (whether the participant is alive or dead) is being measured, publicly available information should be used to determine vital status only as appropriately directed in accordance with local law.

7.3. Lost to Follow-up

A participant will be considered lost to follow-up if the participant repeatedly fails to return for scheduled visits and is unable to be contacted by the study site.

The following actions must be taken if a participant fails to attend a required study visit:

- The site must attempt to contact the participant and reschedule the missed visit as soon as possible. Counsel the participant on the importance of maintaining the assigned visit schedule and ascertain whether the participant wishes to and/or should continue in the study;
- Before a participant is deemed lost to follow-up, the investigator or designee must make every effort to regain contact with the participant (where possible, 3 telephone calls and, if necessary, a certified letter to the participant's last known mailing address or local equivalent methods). These contact attempts should be documented in the participant's medical record;
- Should the participant continue to be unreachable, the participant will be considered to have withdrawn from the study.

8. STUDY ASSESSMENTS AND PROCEDURES

8.1. Administrative Procedures

The investigator (or an appropriate delegate at the investigator site) must obtain a signed and dated ICD before performing any study-specific procedures.

Study procedures and their timing are summarized in the [SoA](#). Protocol waivers or exemptions are not allowed.

Adherence to the study design requirements, including those specified in the [SoA](#), is essential and required for study conduct.

All screening evaluations must be completed and reviewed to confirm that potential participants meet all eligibility criteria. The investigator will maintain a screening log to record details of all participants screened and to confirm eligibility or record reasons for screening failure, as applicable.

Participants will be screened within 28 days prior to administration of the study intervention to confirm that they meet the study population criteria for the study. If the time between screening and dosing exceeds 28 days as a result of unexpected delays (eg, delayed drug shipment), then participants do not require rescreening if the laboratory results obtained prior to first dose administration meet eligibility criteria.

Every effort should be made to ensure that protocol-required tests and procedures are completed as described. However, it is anticipated that from time to time there may be circumstances outside the control of the investigator that make it unfeasible to perform the test. In these cases, the investigator must take all steps necessary to ensure the safety and well-being of the participant. When a protocol-required test cannot be performed, the investigator will document the reason for the missed test and any corrective and preventive actions that they have taken to ensure that required processes are adhered to as soon as possible. The study team must be informed of these incidents in a timely manner.

ECGs and vital sign assessments (pulse rate and BP) should be collected prior to any blood draw. If an IV catheter is utilized for blood sample collections, ECGs and vital sign assessments (pulse rate and BP) should be collected prior to the insertion of the catheter.

For samples being collected and shipped, detailed collection, processing, storage, and shipment instructions and contact information will be provided to the investigator site prior to initiation of the study.

The total blood sampling volume for individual participants in this study is approximately 500 mL. The actual collection times of blood sampling may change. Additional blood samples may be taken for safety assessments at times specified by Pfizer, provided the total volume taken during the study does not exceed 550 mL during any period of 56 consecutive days.

To prepare for study participation, participants will be instructed on the information in the [Lifestyle Considerations](#) and [Concomitant Therapy](#) sections of the protocol.

8.2. Efficacy Assessments

Not applicable.

8.3. Safety Assessments

Planned time points for all safety assessments are provided in the [SoA](#). Unscheduled safety measurements may be obtained at any time during the study to assess any perceived safety issues.

8.3.1. Physical Examinations

A complete physical examination will include, at a minimum, head, ears, eyes, nose, mouth, skin, heart and lung examinations, lymph nodes, and gastrointestinal, musculoskeletal, and neurological systems.

A brief physical examination will include, at a minimum, assessments of general appearance, the respiratory and cardiovascular systems, and participant-reported symptoms.

Physical examinations may be conducted by a physician, trained physician's assistant, or nurse practitioner as acceptable according to local regulation.

Height and weight will also be measured and recorded as per the [SoA](#). For measuring weight, a scale with appropriate range and resolution is used and must be placed on a stable, flat surface. Participants must remove shoes, bulky layers of clothing, and jackets so that only light clothing remains. They must also remove the contents of their pockets and remain still during measurement of weight.

Physical examination findings collected during the study will be considered source data and will not be required to be reported, unless otherwise noted. Any untoward physical examination findings that are identified during the active collection period and meet the definition of an AE or SAE ([Appendix 3](#)) must be reported according to the processes in [Sections 8.4.1 to 8.4.3](#).

8.3.2. Vital Signs

8.3.2.1. Blood Pressure and Pulse Rate

Supine BP will be measured with the participant's arm supported at the level of the heart, and recorded to the nearest mm Hg after approximately 5 minutes of rest. The same arm (preferably the dominant arm) will be used throughout the study. BP should not be taken from the arm with an IV infusion. Participants should be instructed not to speak during measurements.

The same properly sized and calibrated BP cuff will be used to measure BP each time. The use of an automated device for measuring BP and pulse rate is acceptable; however, when done manually, pulse rate will be measured in the brachial/radial artery for at least 30 seconds. When the timing of these measurements coincides with a blood collection, BP and pulse rate should be obtained prior to the nominal time of the blood collection.

Additional collection times, or changes to collection times, of BP and pulse rate will be permitted, as necessary, to ensure appropriate collection of safety data.

Any untoward vital sign findings that are identified during the active collection period and meet the definition of an AE or SAE ([Appendix 3](#)) must be reported according to the processes in [Sections 8.4.1 to 8.4.3](#).

8.3.3. Electrocardiograms

Standard 12-lead ECGs utilizing limb leads (with a 10-second rhythm strip) should be collected at times specified in the [SoA](#) section of this protocol using an ECG machine that automatically calculates the HR and measures PR interval, QT interval, QTcF, and QRS complex. Alternative lead placement methodology using torso leads (eg, Mason-Likar) should not be used given the potential risk of discrepancies with ECGs acquired using standard limb lead placement. All scheduled ECGs should be performed after the participant has rested quietly for at least 5 minutes in a supine position.

To ensure safety of the participants, a qualified individual at the investigator site will make comparisons from the current period to baseline measurements. Additional ECG monitoring will occur if a) a postdose QTcF interval is increased by ≥ 60 ms from the baseline **and** is > 450 ms; or b) an absolute QT value is ≥ 500 ms for any scheduled ECG. If either of these conditions occurs, then 2 additional ECGs will be collected approximately 2 to 4 minutes apart to confirm the original measurement. If the QTcF values from these repeated ECGs remain above the threshold value, then a single ECG must be repeated at least hourly until QTc values from 2 successive ECGs fall below the threshold value that triggered the repeat measurement.

If a) a postdose QTcF interval remains ≥ 60 ms from the baseline **and** is > 450 ms; or b) an absolute QT value is ≥ 500 ms for any scheduled ECG for greater than 4 hours (or sooner, at the discretion of the investigator); or c) QTcF value get progressively longer, the participant should undergo continuous ECG monitoring. A cardiologist should be consulted if QTcF values do not return to less than the criteria listed above after 8 hours of monitoring (or sooner, at the discretion of the investigator).

In some cases, it may be appropriate to repeat abnormal ECGs to rule out improper lead placement as contributing to the ECG abnormality. It is important that leads be placed in the same positions each time in order to achieve precise ECG recordings. If a machine-read QTc value is prolonged, as defined above, repeat measurements may not be necessary if a qualified medical provider's interpretation determines that the QTcF values are in the acceptable range.

ECG values of potential clinical concern are listed in [Appendix 8](#).

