11. Standard 12-lead ECG that demonstrates clinically relevant abnormalities that may affect participant safety or interpretation of study results (eg, QTcF >450 ms, complete LBBB, signs of an acute or indeterminate- age myocardial infarction, ST-T interval changes suggestive of myocardial ischemia, second- or third- degree AV block, or serious bradyarrhythmias or tachyarrhythmias). If the uncorrected QT interval is >450 ms, this interval should be rate-corrected using the Fridericia method only and the resulting QTcF should be used for decision making and reporting. If QTcF exceeds 450 ms, or QRS exceeds 120 ms, the ECG should be repeated twice and the average of the 3 QTcF or QRS values used to determine the participant's eligibility. Computer-interpreted ECGs should be overread by a physician experienced in reading ECGs before excluding a participant.
12. Participants with **ANY** of the following abnormalities in clinical laboratory tests at screening, as assessed by the study-specific laboratory and confirmed by a single repeat test, if deemed necessary:
 - AST **or** ALT level $\geq 1.5 \times$ ULN;

- Total bilirubin level $\geq 1.5 \times$ ULN; participants with a history of Gilbert's syndrome may have direct bilirubin measured and would be eligible for this study provided the direct bilirubin level is \leq ULN.

Other Exclusion Criteria:

13. History of alcohol abuse or binge drinking and/or any other illicit drug use or dependence within 6 months of Screening. Binge drinking is defined as a pattern of 5 (male) or more alcoholic drinks in about 2 hours. As a general rule, alcohol intake should not exceed 14 units per week (1 unit = 8 ounces [240 mL] beer, 1 ounce [30 mL] of 40% spirit, or 3 ounces [90 mL] of wine).
14. Blood donation (excluding plasma donations) of approximately 1 pint (500 mL) or more within 60 days prior to dosing.
15. History of sensitivity to heparin or heparin-induced thrombocytopenia *only if* heparin is planned to flush IV catheters.
16. Total [^{14}C] radioactivity measured in plasma at screening exceeding 11 mBq/mL.
17. Participants with current use of tobacco- and/or nicotine-containing products exceeding equivalent of 5 cigarettes per day.
18. Investigator site staff directly involved in the conduct of the study and their family members, site staff otherwise supervised by the investigator, and sponsor and sponsor delegate employees directly involved in the conduct of the study and their family members.

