9.3.3.2.1. Electrocardiogram Analyses

Changes from baseline for the ECG parameters HR, QTcF, PR interval, and QRS complex will be summarized by treatment and time.

The number (%) of participants with maximum postdose QTcF values and maximum increases from baseline in the following categories will be tabulated by treatment:

[figure not shown]
Safety QTcF Assessment

Degree of Prolongation	Mild (ms)	Moderate (ms)	Severe (ms)
Absolute value	>450-480	>480-500	>500
Increase from baseline		30-60	>60

In addition, the number of participants with uncorrected QT values >500 ms will be summarized.

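### Protocol Section 8.3.3 sets its 500 ms ECG trigger on QT but follows up on QTcF or QTc, so read literally some QTcF values of 500 ms or more mandate no repeat ECG

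*Protocol*

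**What the plan says.** Section 8.3.3 of the protocol treats QT and QTcF as different outputs of the ECG machine, which "automatically calculates the HR and measures PR interval, QT interval, QTcF, and QRS complex". Its additional-monitoring rule has two arms. Arm (a) is a post-dose QTcF rise of at least 60 ms with QTcF above 450 ms. Arm (b) is "an absolute QT value is ≥ 500 ms for any scheduled ECG. If either of these conditions occurs". The later sentence on abnormalities lasting more than 4 hours repeats arm (b), again with QT.

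The steps after the trigger use the corrected interval:

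- Confirmation: "If the QTcF values from these repeated ECGs remain above the threshold value, then a single ECG must be repeated at least hourly"
- Stopping the hourly ECGs: "until QTc values from 2 successive ECGs fall below the threshold value that triggered the repeat measurement"
- Referral: "A cardiologist should be consulted if QTcF values do not return to less than the criteria listed above after 8 hours of monitoring"

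Elsewhere, 500 ms is a QTcF level. Section 9.3.3.2.1 grades QTcF above 500 ms as severe, Appendix 8 lists it as a possible SAE, and SAP Section 6.6.4 lists every participant with a post-dose QTcF above 500 ms. Raw QT has its own separate summary: "the number of participants with uncorrected QT values >500 ms will be summarized".

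**The concern.** The rule is a stated participant-safety threshold, and its steps do not use one interval. Two things follow from the literal text. After an arm (b) trigger, site staff compare a QTcF with a threshold that was set on QT. And because no arm names an absolute QTcF of 500 ms, a participant whose baseline is already fairly high can reach that level without either arm being met. At heart rates above 60 bpm, QT is shorter than QTcF, so a raw-QT threshold becomes less sensitive as the rate rises. Section 2.3.1 lists increased heart rate as a potential risk of this drug class.

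What is at stake is a mandated confirmatory ECG at a level that the protocol itself calls severe. No endpoint, sample size or analysis depends on it.

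**Working it through.** The plan gives no figure to reproduce here, so the check applies the two arms as written.

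**Inputs**
- Arms (a) and (b): Section 8.3.3.
- Rate correction: Fridericia, QTcF = QT / (60/HR)^(1/3), the method named in exclusion criterion 11 (Section 5.2).
- Screening ceiling for QTcF: 450 ms, from the same criterion ("If QTcF exceeds 450 ms, or QRS exceeds 120 ms, the ECG should be repeated twice", with the average of three deciding eligibility).
- Baseline: SAP Section 3.5 takes the last planned pre-dose value in each period and sets no upper limit.
- Heart rate: not given in the documents, so treated as an assumption and varied from 55 to 90 bpm.

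**Condition for a miss.** QTcF ≥ 500, QTcF − baseline < 60, and QT < 500. Since QT = QTcF × (60/HR)^(1/3), the last part means HR > 60 × (QTcF/500)^3:
- QTcF 500: 60 × 1.000^3 = 60.0 bpm
- QTcF 505: 60 × 1.010^3 = 61.8 bpm
- QTcF 509: 60 × 1.018^3 = 63.3 bpm

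**Missed range in whole ms.** The lower end is 500. The upper end is baseline + 59, because a rise of 60 meets arm (a).

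| Baseline QTcF | Missed QTcF | HR above which the whole range is missed |
|---|---|---|
| 440 or less | none | – |
| 441 | 500 | 60.0 |
| 445 | 500-504 | 61.5 |
| 448 | 500-507 | 62.6 |
| 450 | 500-509 | 63.3 |
| 455 | 500-514 | 65.2 |
| 460 | 500-519 | 67.1 |

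The last two rows need a pre-dose baseline above the screening ceiling. At 60 bpm or below nothing is missed, because QT is then at least as long as QTcF and arm (b) is met.

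**Example.** Baseline 448 ms, post-dose QTcF 504 ms at 75 bpm. The rise is 504 − 448 = 56 ms, so arm (a) is not met. QT = 504 × (60/75)^(1/3) = 467.9 ms, so arm (b) is not met. No repeat is mandated.

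**Slow heart rates.** The opposite mismatch bears on the choice of fix. A QT of 500 ms corresponds to QTcF 485.7 ms at 55 bpm, 470.5 at 50 and 454.3 at 45. Arm (b) is met, although QTcF is already under 500. If arm (b) were set on QTcF alone, it would no longer be met by QT of 500-514 ms at 55 bpm, 500 to about 531 at 50, or 500 to about 550 at 45. Arm (a) would catch these only where QTcF had also risen by 60 ms and exceeded 450.

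**With arm (b) on QT or QTcF ≥ 500 ms.** Every QTcF of 500 ms or more meets it by definition, at any baseline and heart rate, and every QT of 500 ms or more still does.

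**The case against.** The strongest reply is that the intended reading is clear. Section 8.3.3 goes on to say "If a machine-read QTc value is prolonged, as defined above", which treats the preceding thresholds as QTc thresholds. The documents elsewhere write 'uncorrected' when they mean raw QT, and apply 'absolute' to QTcF levels (Appendix 8; SAP Appendix 2). On that reading this is an editorial slip. I accept that QTcF was probably meant, but the text says QT twice, and a safety rule should not depend on inference by site staff.

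A second reply is that raw QT was deliberate, since it is also summarised separately. A rule with one QTcF arm and one QT arm would be coherent as a trigger, but it would not explain confirmation, stop and referral on the corrected interval. This reply does carry weight against simply replacing QT with QTcF, which would give up a trigger at slow heart rates.

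A third is that other duties cover the case. QTcF above 480 ms may qualify as an AE and above 500 ms as an SAE (Appendix 8). Recorded events must be followed (Section 8.4.3), with supplemental measurements as medically indicated (Section 10.3.3). Unscheduled safety measurements are allowed, and a progressively lengthening QTcF leads to continuous monitoring. These are real backstops. None is a numeric trigger for a repeat ECG, and progressive lengthening can be seen only with serial ECGs.

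The objection on materiality stands. Section 2.2.4.1 reports no clinically significant adverse ECG trends at single doses up to 200 mg or multiple doses up to 180 mg daily. As far as the broken schedule tables can be read, scheduled post-dose ECGs fall only around discharge or early termination. Section 4.2 expects the drug to have left plasma by Day 7, the earliest discharge day in Period 1 and the discharge day in Period 2.

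**Conclusion.** The point holds as a minor wording fault in a safety rule. The trigger and its follow-up do not use one interval, and the literal text leaves some QTcF values of 500 ms or more without a mandated repeat. The gap needs three things together: baseline QTcF above 440 ms, a rise below 60 ms, and a heart rate above about 60 to 63 bpm (somewhat higher at the top of the range if baseline exceeds 450 ms). The practical effect in about 6 healthy men given single doses is very small, and no endpoint or analysis changes.

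Two stronger readings are tempting. A reader might infer that cardiac monitoring in this study is materially deficient. The documents do not support that, given the evident intent, the backstops, the dose and the ECG record so far. A reader might also take 500-509 ms as the full extent of the gap. That range assumes a baseline of 450 ms. The ceiling applies at screening, and the SAP's pre-dose baseline is not capped, so the range is conditional and not a bound.

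**What to change.** In Section 8.3.3, write arm (b) as *an absolute QT or QTcF value is ≥ 500 ms*, in both the trigger sentence and the 4-hour sentence. Have the confirmation, hourly-stop and consult sentences refer to the interval and threshold that triggered, with QTcF in place of QTc. The separate count of uncorrected QT above 500 ms in Section 9.3.3.2.1 can stay as it is.

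The change is to wording only, since the machine already reports both intervals. It costs an occasional extra confirmatory ECG. Where QT stays at 500 ms or more at a slow heart rate, it may also mean some further hourly ECGs that the present QTcF-based confirmation would end. The existing provision that repeats may be unnecessary when a qualified provider judges QTcF acceptable limits that burden. Setting arm (b) on QTcF alone would also close the gap, but would drop the raw-QT trigger below 60 bpm.
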